8.4. Study Endpoints

8.4.1. Primary Endpoints

- To assess disease severity (Remission, Low Activity, Moderate Activity and High activity) and the mean relative change in Clinical Disease Activity Index (CDAI) among patients with active rheumatoid arthritis treated with Leflunomide as first line therapy and as add-on therapy to other DMARDs (such as Methotrexate, Hydroxychloroquine, Sulfasalazine) with or without Steroids between baseline and week 36.
- To assess the mean relative change in Health Assessment Questionnaire Score (HAQ Disability Index) among patients with active rheumatoid arthritis treated with Leflunomide as first line therapy and as add-on therapy to other DMARDs (such as Methotrexate, Hydroxychloroquine, Sulfasalazine) with or without Steroids between baseline and week 36.

8.4.2. Secondary Endpoints

- Qualitative and quantitative descriptive analysis with (95% confidence intervals) for the below variable :
 - Demographics
 - Medical History
 - o RA severity
 - o RA duration
 - Line of therapy
 - o Daily dose
 - o Treatment duration
 - o Reason for treatment adjustment

Study Protocol: EVA_CLEAR_11022017

• Previous therapies

8.4.3. Safety Endpoints

- To assess the frequency of AEs/SAEs among patients using Leflunomide as first line therapy and as add-on therapy to other DMARDs (such as Methotrexate, Hydroxychloroquine, Sulfasalazine) with or without Steroids and its relation to study medication.
- 8.5. Endpoints Variables

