STATISTICAL CONSIDERATIONS	 The primary objective of CLEAR study is to assess the clinical efficacy of Leflunomide as first line therapy and as add-on therapy to other DMARDs (such as Methotrexate, Hydroxychloroquine, Sulfasalazine) with or without Steroids as measured by the mean relative change in Clinical Disease Activity Index (CDAI) and Health Assessment Questionnaire (HAQ Disability Index) among patients with active rheumatoid arthritis. Considering an alpha error of 5% using two-sided 95% CI of Wilcoxon signed-rank test and a study power of 80%, a sample of 332 patients will be required to detect an effect size of 0.158 between baseline and study endpoint, plus an expected drop-out rate of 20% during the 9 months observational study duration. Thus, a sample of 398 patients will be appropriate that rounded to 400 patients. Randomization method 						
	Not applicable.						
	Statistical methodologies:						
	- Descriptive analysis:						
	 Percent (%) distribution for all categorical variables and 						

	mean with (SD) and median (Minimum: Maximum) for				
	- Comparative analysis:				
	 Student t-test and One Way ANOVA to estimate the comparison between the treatment arms for the numerical variables (according to their distribution; non-parametric substitution tests could be used). 				
	 Paired t-test and repeated measure ANOVA test to estimate the change in numerical variables throughout the study visits (according to their distribution; non-parametric substitution tests could be used). Chi2 test (or Fisher's Exact test) for unpaired and McNemar's test for paired categorical variables. 				
	All tests will be performed on the 5% level of significance.				
	 Any deviation(s) from the original statistical plan will be described in the final report). 				
	 Procedure for accounting for missing, unused, and spurious data will be explained in the statistical analysis plan (SAP). 				
	Interim analysis				
	When approximately the enrolled patients completed 50% of their visits (after Visit 3), an interim analysis for safety and efficacy will be conducted by an independent data monitoring committee. Serious adverse events will be monitored by the committee on an ongoing basis throughout the study.				
	- Protocol planned date: June 2017				
	- First patient In (FPI): September 2017				
	- Last patient In (LPI): December 2017				
ESTIMATED DURATION	- Last patient Out (LPO): September 2018				

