8.5.2. Safety Variables

AE/SAE form to assess frequency of AEs/SAEs among patients.

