8.7. Statistical Analysis Methods

- 8.7.1.Descriptive Analysis
- Percent (%) distribution for all categorical variables and mean with (SD) and median (Minimum: Maximum) for continuous variables according their distribution.

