8.7.2. Comparative Analysis

o Student t-test and One Way ANOVA to estimate the comparison between the treatment

Study Protocol: EVA_CLEAR_11022017 Version Number

arms for the numerical variables (according to their distribution; non-parametric substitution tests could be used).

- Paired t-test and repeated measure ANOVA test to estimate the change in numerical variables throughout the study visits (according to their distribution; non-parametric substitution tests could be used).
- Chi2 test (or Fisher's Exact test) for unpaired and McNemar's test for paired categorical variables.
- All tests will be performed on the 5% level of significance.
- Any deviation(s) from the original statistical plan will be described in the final report.

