10.2. Adverse Events Monitoring

All AEs regardless of seriousness or relationship to Medicinal Product (MP), spanning from the signature of the informed consent form, until the end of the study as defined by the protocol for that patient, are to be recorded on the corresponding page(s) included in the CRF and reported as described in the following sections.

For all adverse events, the investigator must pursue and obtain information adequate to determine the outcome of the adverse event and to assess whether it meets the criteria for classification as a serious adverse event requiring immediate notification to Sponsor or its designated representative.

For all adverse events, sufficient information should be obtained by the investigator to determine the causality of the adverse event. The investigator is required to assess causality. For adverse events with a causal relationship to the MP, Follow-Up by the investigator is required until the event or its sequelae resolve or stabilize at a level acceptable to the investigator, and Sponsor concurs with that assessment. This may imply that observations will continue beyond the last planned visit per protocol, and that additional investigations may be requested by the Monitoring Team up to as noticed by the sponsor

Whenever possible, diagnosis or single syndrome should be reported instead of symptoms. The Investigator should specify the date of onset, intensity, action taken with respect to MP, corrective treatment/therapy given, additional investigations performed, outcome and his/her opinion as to whether there is a reasonable possibility that the AE was caused by the MP.

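### AE/SAE frequency is not tied to time at risk although 20% drop-out is expected, so a percentage alone can understate the 36-week risk

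*Combined protocol and SAP*

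**What the plan says.** Section 8.4.3 sets the safety endpoint: "To assess the frequency of AEs/SAEs among patients using Leflunomide as first line therapy and as add-on therapy to other DMARDs", with its relation to study medication. Section 8.5.2 names the AE/SAE form as the variable, "to assess frequency of AEs/SAEs among patients". Neither section says whether patients or events are counted, over which denominator, or over what time.

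The methods are general lists. Section 8.7.1 gives "Percent (%) distribution for all categorical variables and mean with (SD) and median (Minimum: Maximum) for continuous variables according their distribution". Section 8.7.2 adds "Chi2 test (or Fisher's Exact test) for unpaired and McNemar's test for paired categorical variables", with all tests at the 5% level. No person-time rate or time-to-event method appears, and section 8.3 defines no separate safety set.

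On follow-up, the sample-size paragraph (Synopsis and 8.1) allows for 332 patients "plus an expected drop-out rate of 20% during the 9 months observational study duration". Section 10.2 collects AEs from consent until the end of study for that patient. Section 11.5 says that withdrawn patients are not replaced, and that an AE causing withdrawal is followed until it resolves or stabilises. After the reporting period, section 10.3 requires only SAEs suspected to be related to the product.

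**The concern.** Patients will be observed for different lengths of time. Someone who leaves at week 6 has had one sixth of the planned 36 weeks in which to report an event, but counts as a full patient in a percentage. The result is neither the 36-week risk nor a rate. It is a mixture that depends on how many patients leave and when.

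Identifying the safety profile in both uses of leflunomide is a stated secondary objective (5.3). A percentage reported without follow-up time is likely to be read as the risk over the 9-month course, and under plausible conditions it would be too low. If one group also loses patients faster or earlier than the other, part of any difference in AE percentages between them would come from follow-up and not from treatment.

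**Working it through.** The plan gives no expected AE rate and no precision target for safety, so there is no safety figure to reproduce. Its sample size is an efficacy calculation and does not change here.

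**Inputs from the documents:** drop-out d = 20% (Synopsis, 8.1), follow-up of 36 weeks, planned N = 400.

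**Assumptions:** a constant AE hazard, drop-out unrelated to AEs, a true 36-week risk p (30% as the base case, 10% and 50% as a range), and leavers exiting evenly over the first W weeks, with W = 36 or 12.

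**Formulas**
- Hazard per week: λ = −ln(1 − p)/36
- Mean observed risk in leavers: m = 1 − (1 − exp(−λW))/(λW)
- Expected percentage: (1 − d)p + d·m

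**Base case, p = 30%**
- 36λ = −ln(0.7) = 0.3567.
- W = 36: m = 1 − 0.30/0.3567 = 0.159. Percentage = 0.8 × 0.30 + 0.2 × 0.159 = 27.2%.
- W = 12: λW = 0.1189 and m = 0.057. Percentage = 0.8 × 0.30 + 0.2 × 0.057 = 25.1%.

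In 400 patients that is about 109 or 101 patients with an AE, against 120 under complete follow-up.

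| True 36-week risk | Exit evenly over 36 weeks | Exit evenly over 12 weeks |
|---|---|---|
| 10% | 9.0% | 8.3% |
| 30% | 27.2% | 25.1% |
| 50% | 45.6% | 42.1% |

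In this table the relative understatement is about 9 to 10% for even exit and 16 to 17% for early exit.

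**Between groups.** With the same hazard and the same exit pattern in both groups, the spurious difference is (d₂ − d₁)(p − m). It is zero when drop-out is equal, for example 20% in each. With p = 30%:

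| Assumed drop-out | W = 36 | W = 12 |
|---|---|---|
| 20% v 20% | 0 points | 0 points |
| 15% v 25% | 1.4 points | 2.4 points |
| 10% v 30% | 2.8 points (28.6% v 25.8%) | 4.9 points (27.6% v 22.7%) |

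These drop-out splits are hypothetical. The documents give only the overall 20%.

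**Where the bias vanishes.** If every AE occurs before anyone leaves, or if patients leave only after their first AE, every affected patient is counted and the percentage is right.

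**Check on the person-time rate.** Suppose both groups have a 30% risk, all AEs occur at treatment start, and 10% v 30% drop out evenly over 12 weeks. Mean follow-up is 0.9 × 36 + 0.1 × 6 = 33 weeks against 0.7 × 36 + 0.3 × 6 = 27 weeks. The percentage is correct in both groups, but the rate is 33/27 = 1.22 times as high in the group that leaves faster. The rate therefore cannot simply replace the percentage.

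**The case against.** A reader might infer three stronger things, and the documents support none of them.

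- **That the plan commits to a crude proportion compared by chi-square.** Sections 8.7.1 and 8.7.2 are general lists, no test is assigned to AEs, and the safety objective is descriptive. What stands is that no listed method takes account of time at risk.
- **That a group leaving faster through intolerance would look safer.** A patient who leaves because of an AE has had one. Section 10.7 requires it on the AE page and section 11.5 requires it to be followed, so that patient is counted. The understatement comes from patients who leave for other reasons.
- **That a false first-line versus add-on difference is built in.** That needs drop-out differing in amount or timing, and the plan gives no split by group, timing or reason.

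The bias is also modest. The base-case 2.8 points is smaller than the 95% confidence half-width for 30% in 400 patients, 1.96 × √(0.3 × 0.7/400) = 4.5 points. That is fair, but the bias is systematic, does not shrink with sample size, and reaches 4.9 points with early exit.

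Finally, section 8.8 defers missing-data handling to a SAP. The text at hand contains no such rule, and the sentence does not mention time at risk. A later SAP could close the gap.

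**Conclusion.** The point holds as a gap that is cheap to close. AE/SAE frequency is not linked to time at risk, and the listed methods offer only percentages and tests on them, despite an expected 20% drop-out. At a true 30% risk the understatement is 2.8 points with even exit and 4.9 points with exit in the first 12 weeks. Those sizes rest on a constant hazard and on drop-out unrelated to AEs. They fall towards zero if AEs come early or precede withdrawal. A spurious group difference is possible but conditional on unequal drop-out. The documents give no reason to predict its size or direction, and they do not guarantee equal drop-out in non-randomised groups either. The percentage need not be dropped. It needs a companion estimate that handles early exit.

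**What to change.** In sections 8.4.3, 8.5.2 and 8.7:

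1. Keep n (%) with at least one AE and at least one SAE, among all patients with at least one dose.
2. Add the Kaplan-Meier cumulative incidence of first AE and first SAE to week 36 with 95% CI, overall and by first-line/add-on, as the estimate of 36-week risk.
3. Add events per 100 patient-years with 95% CI as a supplement.
4. Show follow-up time and drop-out by group, so that readers can judge whether the percentages are comparable.

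The cost is a few extra tables. Much of the data is already planned: section 10.2 states "The Investigator should specify the date of onset, intensity, action taken with respect to MP", and treatment duration is a listed variable (8.4.2, 8.6). The data lists in 7.2 do not name first-dose or last-contact dates, and the Study Completion Form is scheduled only at Visit 6, so the sponsor should confirm that the CRF captures both dates for patients who leave early.

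Three limits belong in the report. Kaplan-Meier assumes uninformative censoring. The rate is time-neutral only under a roughly constant hazard. Neither removes confounding between the non-randomised groups.

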8.5.1. Efficacy Variables

- Clinical Disease Activity index (CDAI) in baseline and at week 36 to measure disease severity and relative mean change between study endpoints.
- Health assessment questionnaire (HAQ Disability Index) in baseline and at week 36 to measure relative mean change between study endpoints.

8.5.2. Safety Variables

AE/SAE form to assess frequency of AEs/SAEs among patients.

8.6. Other Covariate/Control Variables

- Management patterns and patients characteristics as described parameters below:
 - Demographics
 - Medical History
 - RA severity
 - RA duration
 - Line of therapy
 - Daily dose
 - Treatment duration
 - Reason for treatment adjustment
 - Previous therapies

8.7. Statistical Analysis Methods

- 8.7.1.Descriptive Analysis
- Percent (%) distribution for all categorical variables and mean with (SD) and median (Minimum: Maximum) for continuous variables according their distribution.

8.7.2. Comparative Analysis

o Student t-test and One Way ANOVA to estimate the comparison between the treatment

Study Protocol: EVA_CLEAR_11022017 Version Number

arms for the numerical variables (according to their distribution; non-parametric substitution tests could be used).

- Paired t-test and repeated measure ANOVA test to estimate the change in numerical variables throughout the study visits (according to their distribution; non-parametric substitution tests could be used).
- Chi2 test (or Fisher's Exact test) for unpaired and McNemar's test for paired categorical variables.
- All tests will be performed on the 5% level of significance.
- Any deviation(s) from the original statistical plan will be described in the final report.

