8.3. Analysis Population

The obtained clinical data will be analyzed on an intention-to-treat basis. Primary analysis will be done by intention-to-treat including all eligible enrolled patients with at least one treatment dose and post first assessment score (CDAI and HAQ) attending any post treatment visit and efficacy variables will be analyzed using the last-observation-carried-forward convention (LOCF).

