8.8. Handling of Missing Values

- Procedure for accounting for missing, unused, and spurious data will be explained in the statistical analysis plan (SAP).

9. Treatment

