9.2. Mode of Administration

Arthfree (Leflunomide 20mg)

Study Protocol: EVA_CLEAR_11022017

Dose: 1 tablet once daily, should be swallowed whole with sufficient amounts of liquids. The extent of Leflunomide absorption is not affected if taken with meals. Doses higher than 20 mg/day are not recommended. Improvement in the rheumatoid condition usually starts after 4 to 6 weeks and may further improve up to 4 to 6 months.

Loading dose: a tablet of Leflunomide 100 mg for three days. should be swallowed whole with sufficient amounts of liquids. The extent of Leflunomide absorption is not affected if taken with meals.

Due to the long half-life in patients with rheumatoid arthritis and recommended dosing interval (24 hours), a loading dose is needed to provide steady-state concentrations more rapidly.

10. Pharmacovigilance

For Safety Reference; this study will be conducted consistent with The International Conference on Harmonization Guideline E2A and 21 CFR Part 312 and WHO Guidelines.

Safety assessments will consist of monitoring and recording adverse events; including serious and non-serious adverse events, measurement of protocol-specified safety laboratory assessments, measurement of Protocol-Specified Vital Signs and other Protocol-Specified Measures that are deemed critical to the safety evaluation of the study.

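### Repeated-measures ANOVA for laboratory values and vital signs has no missing-data rule; its classical form would leave out up to 80 of 400 patients through drop-out alone

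*Combined protocol and SAP*

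**What the plan says.** For change over time, 8.7.2 (repeated in the synopsis) names "Paired t-test and repeated measure ANOVA test to estimate the change in numerical variables throughout the study visits", adding that, depending on the distribution, "non-parametric substitution tests could be used". It does not name the variables, the visits that enter the model, or how incomplete patients are treated.

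The schedules in the synopsis and in 7.2.1 mark laboratory tests (including blood count, AST, ALT, creatinine, glucose, ESR and CRP) and vital signs at all six visits. The opening of Section 10 counts "measurement of protocol-specified safety laboratory assessments, measurement of Protocol-Specified Vital Signs" among the safety assessments.

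On missing data, 8.3 states that "efficacy variables will be analyzed using the last-observation-carried-forward convention (LOCF"). Section 8.5.1 lists only CDAI and HAQ as efficacy variables. For everything else, 8.8 says: "Procedure for accounting for missing, unused, and spurious data will be explained in the statistical analysis plan (SAP"). The document supplied contains no such procedure.

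The synopsis and 8.1 size the study with "plus an expected drop-out rate of 20% during the 9 months observational study duration". Section 11.5 says that withdrawn patients are not replaced.

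**The concern.** Repeated-measures ANOVA is the only named method that analyses all visits jointly. In its classical form it needs a complete set of values from every patient, so one missing visit removes the patient, including the visits that were attended. For CDAI and HAQ, carry-forward fills the gaps. For laboratory values and vital signs nothing does.

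The loss is unlikely to be neutral. Section 10.1.7 foresees test results that lead to discontinuation from the study, and 10.7 foresees withdrawal for adverse events. A patient who leaves after an abnormal result at week 6 or 12 has that result removed from the multi-visit trend. What remains is the trend in patients who tolerated treatment to week 36, which tends to look flatter than the trend in all treated patients.

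**Working it through.** **Inputs from the plan.** Enrolment 400; drop-out 20% over nine months; no replacement; visits at baseline and weeks 6, 12, 20, 28 and 36.

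**Step 1: the plan's own figures.** The 332 evaluable patients reproduce with a Wilcoxon signed-rank calculation (asymptotic relative efficiency 3/π, noncentral t, two-sided 5%, effect size 0.158): n = 332, power 80.1%. The 398 is 332 × 1.2 = 398.4, rounded to 400 for enrolment.

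**Step 2: patients kept by a complete-case ANOVA.** 400 × (1 − 0.20) = 320 kept and 80 left out, if drop-out is the only source of missing visits.

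**Step 3: attended visits left unused.** The plan gives no drop-out timing, so two patterns are assumed. Unused at each visit = attending − 320.

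| Week | Even over 36 weeks: attending (unused) | Equal loss per interval: attending (unused) |
|---|---|---|
| 6 | 386.7 (66.7) | 384 (64) |
| 12 | 373.3 (53.3) | 368 (48) |
| 20 | 355.6 (35.6) | 352 (32) |
| 28 | 337.8 (17.8) | 336 (16) |
| 36 | 320 (0) | 320 (0) |
| Total | 1,773 (173) | 1,760 (160) |

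Unused share: 173 / 1,773 = 9.8%, or 160 / 1,760 = 9.1%.

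**Step 4: occasional missed values (assumed rates).** If each of the five post-baseline values is also missing independently with probability m, complete cases = 320 × (1 − m)^5:

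- m = 2%: 289
- m = 5%: 248
- m = 10%: 189

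Some such gaps are plausible. The synopsis visit overview collects laboratory data at some visits only where applicable, whereas the detailed schedules mark all six.

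**Step 5: direction of the bias, extreme case.** Every input here is assumed. Let 8% of patients have ALT rise by 75 U/L, half of them at week 6 and half at week 12. Let all of them then leave, with the other 12% of drop-out random. Over all 400, the week 6 shift is 0.04 × 75 = 3.0 U/L. Simulation among those attending gives +3.1 at week 6 and +3.3 at week 12. The complete-case value is 0.0 at both, because the example lets every affected patient leave.

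If half of the affected patients stayed, with total drop-out still 20%, completers would show about 0.02 × 75 / 0.80 = 1.9 U/L at week 6. The signal is then reduced but not erased.

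**The case against.** A reader might infer that patients who leave early disappear from the laboratory and vital-sign results altogether, or that the plan has chosen a completers-only safety analysis. The documents support neither reading.

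- The sentence that names the ANOVA also names the paired t-test. A paired test of baseline against a given visit keeps every patient with both values.
- Section 8.7.1 plans "mean with (SD) and median (Minimum: Maximum) for continuous variables according their distribution" with no restriction to completers, so an extreme early value can still appear in a by-visit maximum.
- Section 8.8 defers missing data to a SAP. Complete-case handling is the default of the classical method and is not something the plan declares.
- Laboratory trends are not an endpoint. Sections 8.4.3 and 8.5.2 define safety by the frequency of adverse events. Under 10.1.7 a test result that leads to discontinuation is itself reportable as an adverse event, so that patient is counted there.

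All four points stand, and they limit the concern to the multi-visit analysis. They do not remove it. The plan does not say which visits the paired test compares, and a test of baseline against week 36 would also contain completers only. The non-parametric substitutes are unnamed, and the usual multi-visit one, the Friedman test, also needs complete blocks. The deferred rule does not appear in the text supplied.

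**Conclusion.** The concern holds in limited form. Section 8.7.2 assigns repeated-measures ANOVA to numerical variables across visits, with no missing-data rule for those outside efficacy. In its classical form, and at the plan's own 20% drop-out, the analysis would omit up to 80 of 400 patients and about 9% to 10% of attended post-baseline visits. The percentage rests on assumed drop-out timing. The patient count grows if visits are also missed.

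The multi-visit trend can be biased towards no change when patients leave because of abnormal values. The size of that bias cannot be derived from the documents, and the ALT figures only illustrate the extreme case in which every affected patient leaves. CDAI and HAQ, to which carry-forward applies, and adverse event frequency are not affected. The change is worth making because the omitted data will already have been collected.

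**What to change.** In 8.7.2 and the synopsis, replace repeated-measures ANOVA for laboratory and vital-sign variables with a linear mixed model for repeated measures, specified as follows:

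- all observed post-baseline values, with no carry-forward;
- visit as a categorical factor and the baseline value as a covariate;
- unstructured covariance across visits;
- log transformation for skewed laboratory values.

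Report the number of patients observed at each visit beside the estimates.

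The cost is a wording change and a different software procedure, with no new data. The model assumes that values are missing at random given those observed, a weaker assumption than the complete-case analysis needs. It cannot recover patients with no post-baseline value: about 13 of 400 if drop-out is spread evenly (400 − 387 attending week 6). The per-visit counts will make that visible.

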8.1. Determination of Sample Size

The primary objective of CLEAR study is to assess the clinical efficacy of Leflunomide as first line therapy and as add-on therapy to other DMARDs (such as Methotrexate, Hydroxychloroquine, Sulfasalazine) with or without Steroids as measured by the mean relative change in Clinical Disease Activity Index (CDAI) and Health Assessment Questionnaire (HAQ Disability Index) among patients with active rheumatoid arthritis.

Considering an alpha error of **5%** using two-sided 95% CI of Wilcoxon signed-rank test and a study power of **80%**, a sample of **332 patients** will be required to detect an effect size of **0.158** between baseline and study endpoint, plus an expected **drop-out rate of 20%** during the 9 months observational study duration. Thus, a sample of **398 patients** will be appropriate that rounded to **400 patients**.

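### CDAI change and HAQ-DI change are both primary at 5%, with no rule on whether one or both must succeed, and the 80% power belongs to a single test assigned to neither

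*Combined protocol and SAP*

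**What the plan says.** Section 8.4.1, repeated in the Synopsis, has two primary bullets. The first reads "To assess disease severity (Remission, Low Activity, Moderate Activity and High activity) and the mean relative change in Clinical Disease Activity Index (CDAI"), so it contains two measures. The second reads "To assess the mean relative change in Health Assessment Questionnaire Score (HAQ Disability Index"). Both run from baseline to week 36, and neither is ranked above the other.

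Section 8.1 describes the primary objective "as measured by the mean relative change in Clinical Disease Activity Index (CDAI) and Health Assessment Questionnaire (HAQ Disability Index"). It then gives one calculation, a Wilcoxon signed-rank test at two-sided 5% with 80% power. In the words of the Synopsis, "a sample of 332 patients will be required to detect an effect size of 0.158 between baseline and study endpoint". The figure of 398 is then reached for drop-out and rounded to 400. The effect size carries no scale, standard deviation or source.

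On testing, section 8.7.2 says "All tests will be performed on the 5% level of significance". For within-patient numerical change it lists the paired t-test and repeated-measures ANOVA, with non-parametric substitutes allowed. Section 8.3 limits the primary analysis to treated patients with a post-treatment score and adds that "efficacy variables will be analyzed using the last-observation-carried-forward convention (LOCF").

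No section gives a testing order, an alpha split, an adjustment, or a rule on how many primary results must succeed. Section 8.8 leaves only the treatment of missing, unused and spurious data to a separate SAP.

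**The concern.** If one of the two changes is significant at week 36 and the other is not, the plan does not say whether the primary objective was met. That decision could then be taken with the results in hand.

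The two possible rules have different costs. If either change is enough, two tests at 5% give more than a 5% chance of at least one false positive when neither scale has changed. If both are needed, the error rate is safe, but the 80% in section 8.1 no longer describes the chance of success, because it is the power of one test. A reader cannot tell which rule the figures were meant to serve.

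**Working it through.** **Inputs from the documents (section 8.1 and Synopsis):** Wilcoxon signed-rank test, two-sided 5%, power 80%, effect size 0.158, 332 patients needed, 400 to be enrolled.

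**Assumptions, not in the documents:** the true effect on each scale (0.158, 0.20 or 0.25), and the correlation between the two test statistics (0 to 0.7, with 0.9 for the error rate).

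**1. Reproduce the plan's figure.** Use noncentral-t power for a paired test, with n multiplied by the Wilcoxon relative efficiency 3/π.
- Effective n = 332 × 3/π = 317.0.
- Noncentrality = 0.158 × √317.0 = 2.81.
- Power = 80.1%, and 332 is the smallest n that reaches 80%. At 400 the same formula gives 86.9%.

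So the stated 80% is the power of exactly one test.

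**2. If either change suffices.** Family-wise error when neither scale changes = 1 − P(|Z1| ≤ 1.96 and |Z2| ≤ 1.96). At correlation 0 this is 1 − 0.95² = 9.75%. From the bivariate normal:

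| Correlation | 0 | 0.3 | 0.5 | 0.7 | 0.9 |
|---|---|---|---|---|---|
| Family-wise error (%) | 9.75 | 9.51 | 9.07 | 8.35 | 7.0 |

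**3. If both are needed.** Joint power = Φ₂(Φ⁻¹(p1), Φ⁻¹(p2); correlation), where p1 and p2 are the single-test powers. At correlation 0 with 0.158 on both scales it is 0.8009² = 64.1%.

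**4. Chance of a split.** P(exactly one significant) = p1 + p2 − 2 × joint power. For the same case: 80.09 + 80.09 − 2 × 64.14 = 31.9%.

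Results, with correlation 0 / 0.3 / 0.5 / 0.7 in each cell:

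| Analysed | Effects on the two scales | Joint power (%) | Split (%) |
|---|---|---|---|
| 332 | 0.158 and 0.158 | 64.1 / 66.7 / 68.8 / 71.4 | 31.9 / 26.7 / 22.5 / 17.4 |
| 332 | 0.158 and 0.25 | 79.6 / 79.8 / 79.9 / 80.0 | 20.3 / 19.9 / 19.6 / 19.3 |
| 332 | 0.20 and 0.20 | 89.1 / 89.7 / 90.2 / 91.1 | 10.6 / 9.5 / 8.3 / 6.7 |
| 332 | 0.25 and 0.25 | 98.7 / 98.7 / 98.8 / 98.8 | 1.3 / 1.3 / 1.2 / 1.0 |
| 400 | 0.158 and 0.158 | 75.5 / 77.1 / 78.5 / 80.3 | 22.8 / 19.6 / 16.7 / 13.1 |

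The last row is the upper limit under section 8.3, with LOCF keeping every enrolled patient. Even then, with 0.158 on both scales, joint power reaches 80% only at a correlation of about 0.7 or more. The smallest number analysed for 80% joint power in that case is 435, 424, 413 or 397 at correlation 0, 0.3, 0.5 or 0.7.

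**The case against.** The strongest reply is that 0.158 is the smallest effect the study is sized to detect, not a forecast. If both true effects are larger, splits become uncommon (10.6% to 6.7% at 0.20 on both scales) and then rare (about 1% at 0.25). This stands as a limit on the size of the problem. It does not supply the missing rule, and if only one scale exceeds 0.158 the split chance at 332 stays near 20%.

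A second reply is that this is an uncontrolled observational study whose endpoints are worded as assessments, with no stated success criterion, and that naming both scales in section 8.1 simply means both will be reported. It is true that a significant result would show change from baseline only, not a treatment comparison. But the plan does set an alpha, a power and significance tests for efficacy, so the reader needs to know what the 5% and the 80% refer to.

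Two stronger readings are tempting. One is that the error rate is certainly inflated. The documents do not support this: the wording in 8.1 can be read as requiring both changes, and then 5% holds. The other is that the CDAI category is a third formal test that inflates the error further. No test is assigned to it by name, section 8.1 leaves it out of the objective, section 8.7.1 provides percentages for categorical variables, and the category is derived from CDAI itself.

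**Conclusion.** The gap is real and should be fixed. Two primary changes are tested at 5% each without a decision rule, and the 332 patients and 80% power belong to one test that is tied to neither scale. Read one way, the error for the pair is 9.75% to 8.35% (7.0% at correlation 0.9). Read the other way, joint power at 332 is 64.1% to 71.4% with 0.158 on both scales.

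These sizes rest on assumed correlations and effects. A reader might infer that the study is underpowered or that a split is likely. The documents do not support either as a general statement, because they do not state the true effects, and at 0.25 on both scales joint power is near 99%. What holds in every case is that the plan does not say how a split would be classified.

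**What to change.** In sections 8.4.1 and 8.7.2, test the mean relative change in CDAI at week 36 first, at two-sided 5%, with the Wilcoxon signed-rank test used for sizing. Test the mean relative change in HAQ-DI at two-sided 5% only if CDAI succeeds. Report the four-level CDAI category descriptively. CDAI comes first because section 8.1 names it first; the sponsor may have a better reason for an order and should state it. In section 8.1, say that the 80% is the power of the single first-ranked test, and give the scale and the justification for 0.158. The documents supply neither, so relabelling alone is not enough. Carry the same wording into the Synopsis.

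This adds no patients and holds the error for the pair at 5%. If 0.158 is justified for CDAI, that test keeps 80.1% power at 332. The downside is that HAQ-DI can be claimed only if CDAI succeeds, so its chance of being claimed equals the joint power shown above.

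An acceptable alternative is to declare the two changes co-primary, both needed, and to restate joint power in 8.1 with the assumed effect on each scale, the correlation and the number analysed. This is also wording only if the lower power is accepted. Joint power of 80% with 0.158 on both scales would need 397 to 435 analysed patients, which is nearly all of the planned 400 or more than that.
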